## 3.1 Inclusion Criteria

3.1.1 Patients must have a prior diagnosis of Grade IV glioma (Glioblastoma) per 2016 WHO criteria that has progressed after standard radiotherapy (RT) and Temozolomide (TMZ).

(*Note: Pathology will need to be reviewed locally but registration can occur based on pathology report*).

- 3.1.2 Patients must have had radiographic evidence of tumor progression by brain MRI or CT scan with contrast.
- 3.1.3 Prior therapy with gamma knife or other focal high-dose radiotherapy is allowed, but the patient must have subsequent histologic documentation of recurrence, unless the recurrence occurs remote from the treated site.
- 3.1.4 Patients must be surgical resection candidates.
- 3.1.5 Patients must have had no more than 3 prior lines of chemotherapy. This includes the initial treatment and two relapses. Concurrent and adjuvant TMZ-based chemotherapy, including the combination of TMZ with another agent, is considered one line of chemotherapy. For clarification, please contact the PI, [name] at [contact]
- 3.1.6 Patients must be age  $\geq$  18 years. Both male and female are eligible.
- 3.1.7 Patients must exhibit a KPS  $\geq$  70 (Appendix C).

•

•

- 3.1.8 Life expectancy of  $\geq$  12 weeks (per treating investigator's discretion).
- 3.1.9 Patients must be on a stable or decreasing dose of corticosteroids within 5 days prior to CT scan or MRI (which is done to determine eligibility). Patients must be on no more than 8 mg a day but an attempt should be made to keep the dose at 4 mg or less. Please contact the PI if doses of > 4 mg are needed.
- 3.1.10 Patients must have adequate organ and bone marrow function within 14 days prior to registration, as defined below.

(Note: The CBC and chemistries will be repeated within 72 hours of 1st dose of study treatment if baseline tests were more than 7 days prior to dosing).

- leukocytes  $\geq$  3,000/mcL
- absolute neutrophil count  $\geq 1,500/mcL$ 
  - platelets  $\geq 100,000/mcl$
- hemoglobin (Hb) >10.0 g/dL (can be transfused to this level)
- INR, PT, or APTT as follows:
  - In the absence of therapeutic intent to anticoagulate the patient:
    - INR < 1.5, or
    - PT < 1.5×ULN, or
    - $aPTT < 1.5 \times ULN$
    - In the presence of therapeutic intent to anticoagulate the patient:
      - INR or PT and aPTT within therapeutic limits (according to the medical standard in the institution) and the patient has been on a stable dose of anticoagulants for at least 2 weeks before registration.
- total bilirubin  $\leq 1.5 \text{ x ULN}$  (except in patients with Gilbert's disease)
- AST (SGOT)/ALT (SPGT)  $\leq 2.5$  x institutional upper limit of normal (ULN)
  - Serum creatinine < 1.5 x ULN
- Serum creatinine CL >40 mL/min by the Cockcroft-Gault formula

#### IRB #: STU00202283-MOD0025 Approved by NU IRB for use on or after 2/8/2019 through 1/6/2020. (Cockcroft and Gault 1976) or by 24-hour urine collection for determination of

creatinine clearance:

Males: Creatinine CL (mL/min)	$\frac{\text{Weight (kg) x (140 - Age) x 1.0}}{72 \text{ x serum creatinine (mg/dL)}}$
Females: Creatinine CL (mL/min)	$\frac{\text{Weight (kg) x (140 - Age) x 0.85}}{72 \text{ x serum creatinine (mg/dL)}}$

3.1.11 Females of child-bearing potential (FOCBP) and males must agree to use adequate contraception (e.g. hormonal or barrier method of birth control – see appendices acceptable birth control methods) prior to registration, for the duration of study participation, and for 180 days after the last dose of MEDI4736 + tremelimumab combination therapy or 90 days after the last dose of MEDI4736 or tremelimumab monotherapy. Should a female patient become pregnant or suspect she is pregnant while participating in this study, she should inform her treating physician immediately.

*NOTE:* A FOCBP is *any woman* (regardless of sexual orientation, having undergone a tubal ligation, or remaining celibate by choice) who meets both of the following criteria:

- *Has not* undergone a hysterectomy or bilateral oophorectomy.
- *Has had* menses at any time in the preceding 12 consecutive months (and therefore has not been naturally postmenopausal for > 12 months).
- 3.1.12 FOCBP must have a negative pregnancy test (serum or urine) within 7 days prior to registration on study.
- 3.1.13 Patients must have the ability to understand and the willingness to sign a written informed consent prior to registration on study.
- 3.1.14 Subject is willing and able to comply with the protocol for the duration of the study including undergoing treatment and scheduled visits and examinations including follow up.
- 3.1.15 Patients must have given written, signed and dated informed consent prior to registration on the study. NOTE: no study-specific screening procedures may be performed until consent has been given.

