## **3.0 PATIENT ELIGIBILITY**

The target population for this study is patients with recurrent glioblastoma. This will be a single-center trial conducted at neuro-oncology clinic of Northwestern University.

A total of 30 evaluable subjects will be needed for this trial. The accrual cap is 45 patients, in order to cover those patients that do not make it to the first evaluable time point. Hence, the total accrual per arm will be up to 15. Approximately 4 potentially eligible patients are seen per month, and it is anticipated that at least 2 per month will be accrued. Potential patients may be referred to the Principal Investigator (PI) at Northwestern University, [name], at [contact].

Eligibility will be evaluated by the study team according to the following criteria. Eligibility waivers are not permitted. Subjects must meet all of the inclusion and none of the exclusion criteria to be registered to the study. Study treatment may not begin until a subject is registered.

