# 5.0 STUDY PROCEDURES

## 5.1 Pre-Surgery & Surgery

Assessment/Activity	Screening & Baseline 	14 days (+/- 3 d) prior to surgery	Within 7 days prior to Surgery	Day of surgery	Within 72 hours Post- surgery
Informed Consent 	Х				
Review of eligibility criteria	Х				
Medical History	Х				
Concomitant Medications	Х		Х	Х	Х
Neurologic and Physical Exam 	Х		Х		Х
KPS	Х		Х		
Serum or Urine Pregnancy Test	Х				
Brain MRI or CT with contrast 	Х				$X^4$
CBC with diff & clinical chemistry 	Х	X	Х		
Magnesium and Phosphorus	Х	X	Х		
Thyroid testing 	Х				
PTT/PT/INR 	Х				
12-lead ECG 	Х				
Urinalysis with micro	Х				
Creatinine Clearance	Х				
Hepatitis serologies 	Х				
Toxicity assessment	Х			Х	Х
1 st Dose Study Treatment 		X 			
Archival Tissue for research 	X				
Fresh Tissue for research				X 	
Blood for research 		X		X	

 Includes vital signs (pulse, temperature, blood pressure, & weight). Height required at baseline only. On the first day of treatment, vital signs will be measured within an hour prior to start of initial study drug administration, at 30 minutes during the infusion (± 5 minutes), at the end of infusion (+ 5 minutes), and at 30 and 60 minutes (± 5 minutes each) post-infusion. If the infusion takes longer than 60 minutes, blood pressure and pulse measurements should follow the principles described here or more frequently if clinically indicated.

 Baseline procedures (with the exception of informed consent and archival tissue) must be obtained within 14 days of registration. The CBC and chemistries will be repeated within 72 hours of 1 st dose of study treatment if baseline tests were more than 7 days prior to dosing.

 Informed consent should be obtained within 28 days prior to registration.

- IRB #: STU00202283-MOD0025 Approved by NU IRB for use on or after 2/8/2019 through 1/6/2020. The baseline MRI can be up to 21 days prior to registration. The post-surgical MRI of brain should be done within 72 hours after surgery.
-  Twelve-lead ECGs will be obtained after the subject has been resting in a supine position for at least 5 minutes. ECG will be in triplicate (taken 2-5 minutes apart).

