-  Patients will receive one dose of tremelimumab 75 mg (if on Arm 1), MEDI4736 750 mg (if on Arm 2) or the combination of both (if on Arm 3) approximately 2 weeks (14 days +/- 7 days) before surgery.
-  Tumor from prior surgeries will be requested on all patients. Tissue will be analyzed in the [name] Laboratory. Please refer to Section 9.3 and laboratory manual for details.
-  Blood samples will be collected for various research tests at 1 st pre-operative treatment, day of surgery, C1D1 and at each adjuvant treatment imaging visits (i.e. every 2 cycles or 8 weeks):
  - a) 10ml blood in one 10ml Sodium heparin tube: To be collected and processed by the [name] lab for peripheral blood lymphocytes (PBLs).
  - b)8m (2x4ml) blood in two 5ml EDTA (purple top) tubes: To be collected and processed by the [name] lab for gene expression profile using mononuclear cells.
  - c) 10ml blood in one 10ml red top tube: To be collected and processed by the [name] lab for analysis of tryptophan catabolites and cytokines.

Please refer to section 9.0 and laboratory manual for more details

 Chemistries should include electrolytes, calcium, , albumin, alkaline phosphatase, bilirubin (total), SGPT(ALT), SGOT(AST), serum creatinine, and BUN.

 TSH, T4, T3

 Required at baseline only but may be repeated as clinically indicated thereafter.

 Includes hepatitis A antibody, hepatitis B (HBsAg reactive), and Hepatitis C (HCV RNA [qualitative] detection).

 Please refer to Section 9.1 and the laboratory manual for details.

Time Period	Adjuvant Treatment 		Off Treatment			
Assessment/Activity	Cycle 1 Day 1  (+/- 2d)	Cycle 2 Day 1 (+/- 2d)	Cycle 3+ Day 1 (+/- 2d)	Treatment Discontinuation	90 Days Post Last Dose (+/- 7d)	Follow-up 
Concomitant medications	X	X	X			
Toxicity assessment	Х	Х	X	X	X	
Neurological exam and KPS 	Х	X	X	Х	Х	
Vital signs & weight 	X	X	X			
CBC with diff 	X		X	X	Х	
Comprehensive Chemistry Panel	X	X	X	X	Х	
Thyroid Function Tests 	X		X	X	Х	
ECG 	X			X		
Tumor Imaging (MRI/CT)	X 		X 	X 		
Tremelimumab monotherapy 	Х	X	X			
MEDI4736 monotherapy 	X	X	X			
Combination therapy 	X	X	X 			
Research tissue		X 	·			·

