### **11.3 Registration Procedures**

BEFORE a patient can be treated on study, please complete and submit the following items to confirm eligibility and receive a subject identification number:

- Eligibility eCRF (complete in NOTIS)
- Eligibility checklist (signed and dated by the treating physician upload in NOTIS)
- Signed and dated informed consent document (upload in NOTIS)
- Pathology Report (upload in NOTIS)

The QAM will review the registration, register the patient, assign an identification number, and send a confirmation of registration to involved personnel. Registration will then be complete and the patient may begin study treatment.

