Section 3.1.7	Specifications for patients on some drugs to be included in the14 study.	Has been converted to exclusion criteria 3.2 .6 All other footnotes re- numbered to match the changes.	For clarity

Section 3.1.12 (now 3.1.10) inclusion criteria	The baseline blood tests for organ and bone marrow function were required to be done within 7 days of registration	The window has been extended to 14 days. A note has been added: "The CBC and chemistries will be repeated within 72 hours of 1 st dose of study treatment if baseline tests were more than 7 days prior to dosing."	For convenience
Section 3.2.15 Exclusion criteria	Patients with a history of active malignancy within 3 years prior to registration. Note: exceptions to this requirement include adequately treated non- melanoma skin cancer or lentigo maligna or carcinoma in situ without evidence of disease	Added prostate cancer to this list of exceptions: "prostate cancers with a Gleason score < 8 and with prostatectomy and no lymph node involvement."	For ease of enrollment
Section 4.4 Events requiring dose modifications	List of events requiring dose modifications anytime during the study.	Removed this section	Conflicts with information provided in section 4.5, which also lists dose delays/modifications.
Section 5.1 Study procedures table for pre- surgery and surgery	Footnote 9 has list of serum chemistries which included magnesium and phosphorus	Removed magnesium and phosphorus from this list and inserted them in a separate row in the table.	For clarity and convenience, since magnesium and phosphorus are not part of the routine serum chemistry.
	Informed consent was to be obtained within 14 days of registration	Informed consent to be obtained within 28 days of registration. Footnote 2 and 3 updated to reflect this.(Footnote 3 was earlier related to MRI but is now redundant. So this was deleted and updated with information regarding ICF).	For convenience.
Section 6.2 Secondary endpoints	Secondary endpoints stated	Language added to state evaluable subjects for each endpoint. Also, language updated to be consistent with section 2	For clarity and consistency

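### The only scheduled pregnancy test is tied to registration, and nothing limits its age at the first dose

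*Combined protocol and SAP*

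**What the plan says.** Criterion 3.1.12 reads: "FOCBP must have a negative pregnancy test (serum or urine) within 7 days prior to registration on study". Registration is the only date to which the test is tied.

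Section 3.0 states the order of events, "Study treatment may not begin until a subject is registered", and section 11.3 repeats it from the other side: "Registration will then be complete and the patient may begin study treatment". Neither says how soon after registration the first dose must be given. The first dose is timed to surgery, about 14 days beforehand (sections 4.2 and 5.1).

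In the 5.1 schedule the row "Serum or Urine Pregnancy Test" has one mark, under screening and baseline. The row "CBC with diff & clinical chemistry" is marked there too, and again at the first-dose visit. The 5.2 schedule for the adjuvant period lists laboratory tests such as "Comprehensive Chemistry Panel" but has no pregnancy-test row.

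For CBC and chemistries there is a rule tied to dosing. The note to 3.1.10, repeated in footnote 2 of 5.1, asks for a repeat within 72 hours of the first "dose of study treatment if baseline tests were more than 7 days prior to dosing". The note does not mention the pregnancy test.

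**The concern.** Pregnancy is an exclusion (3.2.19), and section 7.2.7 bars further doses once a subject is pregnant. The first dose is the last point at which fetal exposure can be avoided altogether, yet no test is tied to it. A pregnancy too early to detect at screening, or one that begins afterwards, could go unnoticed at dosing, and the chance of that grows with the time since the test.

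Registration and first dose need not be close together. The first dose depends on the surgical date. Several waiting periods also run to the first dose and not to registration: radiotherapy (3.2.5), prior systemic agents (3.2.6), other investigational agents (3.2.8) and the two-week anticonvulsant wash-out (3.2.9). As written, a patient could be registered before such a period has fully run, so a gap of some days is plausible.

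What is at stake is participant safety at one dose. No endpoint, estimand or analysis depends on it.

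**Working it through.** The plan gives no figure for the age of the test at first dose, so there is none to reproduce. The check is date arithmetic.

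**Inputs**

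- s = days from pregnancy test to registration. Allowed range 0 to 7 (3.1.12).
- g = days from registration to first dose. At least 0 (3.0, 11.3); no upper limit stated. All values of g below are assumptions.
- Footnote 2 of 5.1 gives baseline procedures in general 14 days before registration. The stricter 7 days in 3.1.12 governs the pregnancy test, so s stays at 7 or less.
- The timing of the first dose relative to surgery does not bound g, because surgery is not tied to registration either.

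**Formula**

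Age at first dose = s + g. The largest compliant value is 7 + g.

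**Results in days, for illustrative s and assumed g**

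| s | g = 0 | g = 3 | g = 7 | g = 14 |
|---|---|---|---|---|
| 1 | 1 | 4 | 8 | 15 |
| 4 | 4 | 7 | 11 | 18 |
| 7 (worst case) | 7 | 10 | 14 | 21 |

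The age passes 7 days only when s + g > 7. That happens in 7 of these 12 cells: none of 3 at g = 0, one of 3 at g = 3, and all 3 at both g = 7 and g = 14 (0 + 1 + 3 + 3 = 7). The count describes the chosen grid and is not a probability. A short s can absorb a moderate gap: s = 1 with g = 6 gives 7 days.

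**With a conditional repeat**

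If s + g is 7 or less, the original test stands and is at most 7 days old. If s + g is more than 7, the repeat is at most 72 hours, or 3 days, old. The oldest compliant test at first dose is then 7 days for every g.

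**The case against.** The strongest reply is that this is a choice of anchor and contradicts nothing in the plan. Registration is the eligibility gate throughout, and 7 days is tighter than the 14 days for baseline procedures generally or the 21 days for the MRI. If patients are dosed on the day of registration, there is no excess at all.

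Other provisions also cover the interval:

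- contraception agreed before registration and a duty to report a suspected pregnancy at once (3.1.11);
- exclusion of those not using effective birth control (3.2.19);
- two methods from screening for sexually active women with a non-sterilised partner (4.3.2);
- removal of a patient who becomes pregnant or wishes to (4.7), and no further dosing (7.2.7).

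The CBC repeat rule proves no oversight. Appendix D, Amendment 4, shows that it arrived when the laboratory window was relaxed: "The window has been extended to 14 days". The pregnancy window was not widened, so there was nothing to offset.

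Nor does the text show specific fetal harm. The tremelimumab monkey study in 1.4.1 found no maternal or developmental toxicity. No such study is described for MEDI4736, given in Arms 2 and 3, but the protocol refers to an Investigator's Brochure that is not available here, so that silence carries little weight.

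Finally, a 7-day cap does not exclude a very early pregnancy, and it adds nothing for later doses over up to 24 months.

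Most of this stands, and it is why the point is minor. None of it supplies a rule on the age of the test at dosing. Contraception depends on adherence, and the protocol itself asks for a test in addition to contraception. Prompt dosing may be usual, but nothing requires it; where it happens, the repeat would seldom be triggered.

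**Conclusion.** The concern holds, as a minor one. Followed exactly, the plan permits a first dose on a pregnancy test of any age from 0 to 7 + g days, with no stated limit on g. The worst case is 7 days if dosing is on the day of registration, and 14 or 21 days if g is 7 or 14.

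The finding that no limit exists rests on the text of 3.0, 3.1.12, 5.1, 5.2 and 11.3; the study schema figure and a few removed pages could not be read. Every age above 7 days rests on an assumed g. The number of women of childbearing potential among the up to 45 patients is not given, so the number affected cannot be estimated. The conclusion is confined to the first dose.

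**What to change.** Keep the present sentence of 3.1.12 and add: *If this test was taken more than 7 days before the first dose of study treatment, it will be repeated and must be negative within 72 hours before that dose.* Put the same sentence in a footnote to the pregnancy-test row of 5.1, with a conditional mark in the first-dose column. The CBC and chemistry note in 3.1.10 is a ready model for the wording.

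The cost is one sentence, one footnote and one further urine or serum test for some women. It can be done alongside the CBC and chemistries already scheduled at the first-dose visit, so no extra visit is needed.

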## 3.2 Exclusion Criteria

- 3.2.1 Involvement in the planning and/or conduct of the study (applies to both AstraZeneca staff and/or staff at the study site); Previous enrolment or randomization in the present study.
- 3.2.2 Has received prior therapy with an anti-PD-1, anti-PD-L2, anti-CD137, or anti-Cytotoxic T-lymphocyte-associated antigen-4 (CTLA-4) antibody (including ipilimumab or any other antibody or drug specifically targeting T-cell co-stimulation or checkpoint pathways).
- 3.2.3 Has known active Hepatitis B (e.g., HBsAg reactive) or Hepatitis C (e.g., HCV RNA [qualitative] is detected).
- 3.2.4 Known active human immunodeficiency virus (HIV1/2 antibodies).
- 3.2.5 Treatment with radiation therapy within 12 weeks prior to the first dose of study treatment, unless there is tissue confirmation of tumor recurrence or there is progression outside the treatment field.

IRB #: STU00202283-MOD0025 Approved by NU IRB for use on or after 2/8/2019 through 1/6/2020.
 3.2.6 Administration of any of the following within the specified timeframe prior to the first dose of study drug:

- 4 weeks for TMZ,
- 6 weeks for nitrosoureas,
- 3 weeks for a biologic or targeted agent (i.e. small molecule)
  - 4 weeks for a VEGF inhibitor (i.e. bevacizumab)
- 3.2.7 Patient has history of primary immunodeficiency OR has received any other form of immunosuppressive therapy within 7 days prior to the first dose of trial treatment, excluding intranasal and inhaled corticosteroids or systemic corticosteroids at physiological doses. Attempts should be made to have patient on lowest possible dose of steroids (acceptable range4-8 mg. please contact PI if dose is >4 mg), and weaned to off as is feasible.
- 3.2.8 Patients receiving any other investigational chemotherapeutic agents within 28 days prior to the first dose of trial treatment.
- 3.2.9 Patients on an enzyme-inducing anti-convulsant who cannot be switched to a nonenzyme-inducing anti-convulsant with a 2 week wash-out period from time of drug discontinuation until Day 1 of study treatment.
- 3.2.10 Mean QT interval corrected for heart rate (QTc) ≥470 ms calculated from an electrocardiograms (ECGs) using Bazett's Correction. If first ECG is abnormal, then the mean will be calculated from 3 consecutive ECGs (taken 2-5 minutes apart). Please contact the PI for further clarification.
- 3.2.11 Active or prior documented history of immunologic disorder including autoimmune disease within the past 2 years NOTE: Subjects with vitiligo, Grave's disease, or psoriasis not requiring systemic treatment (within the past 2 years) are not excluded.
- 3.2.12 Active or prior documented inflammatory bowel disease (e.g., Crohn's disease, ulcerative colitis).
- 3.2.13 History of allogeneic organ transplant.
- 3.2.14 Uncontrolled intercurrent illness including, but not limited to:
  - ongoing or active infection,
  - symptomatic congestive heart failure,
  - uncontrolled hypertension
  - unstable angina pectoris,
  - cardiac arrhythmia,
  - active peptic ulcer disease or gastritis,
  - active bleeding diatheses, or
  - psychiatric illness/social situations that would limit compliance with study requirements or compromise the ability of the subject to give written informed consent.
- 3.2.15 Known history of previous clinical diagnosis of tuberculosis.
- 3.2.16 History of leptomeningeal carcinomatosis.
- 3.2.17 Patients with a history of active malignancy within 3 years prior to registration. Note: exceptions to this requirement include adequately treated non-melanoma skin cancer or lentigo maligna or carcinoma in situ without evidence of disease or prostate cancers with a Gleason score < 8 and with prostatectomy and no lymph node involvement.
- 3.2.18 Receipt of live attenuated vaccination within 30 days prior to study entry (or due to receive one within 30 days of receiving either MEDI4736 or tremelimumab).
- 3.2.19 Female subjects who are pregnant, breast-feeding or male or female patients of

IRB #: STU00202283-MOD0025 Approved by NU IRB for use on or after 2/8/2019 through 1/6/2020. reproductive potential who are not employing an effective method of birth control.

- 3.2.20 Any condition that, in the opinion of the investigator, would interfere with evaluation of study treatment or interpretation of patient safety or study results.
- 3.2.21 Subjects with uncontrolled seizures.
- 3.2.22 Patients who have a history of allergic reactions attributed to compounds of similar chemical or biologic composition to MEDI3475 are not eligible.

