#### 1.1.2 Glioblastoma

For clinical trials in glioblastoma (GBM), many have looked at target specific agents added to standard therapy; however none of them has been of benefit to date. There've also been a few trials looking at patients with an unmethylated MGMT promoter but none have shown a significant impact in this patient population, but it remains a group where more work is needed.

More novel approaches in oncology and in neuro-oncology are to use immunologic therapies. In GBM, there are vaccine therapies that are either derived from the patient's known tumor (HSPPC-96) or are designed to target specific epitopes on the tumor cells such as EGFRvIII (CDX-110) or a number of other epitopes (ICT-107) targeted by other vaccines. Phase II data using CDX-110, ICT 107, HSPPC-96 and others have shown some promise. While preliminary data looks promising with these agents, the most advanced has not proven effective in a randomized phase 3 study (ICT-107) (Press Release) but data will be emerging on CDX-110 as the trial is completing enrollment.

Currently there are several agents under investigation that target the local tumor immuneprotection in solid tumors-particularly melanoma, such CTLA-4 blockade, PD1 and PDL1 blockade. While the majority of trials have occurred in melanoma, there is recent data in other cancers such as renal cell and small cell lung cancer 4.5,6. While expected in melanoma and renal cell due to immunologic aspects of these diseases, the efficacy in other tumors was less clear but benefit has been shown in lung cancer. Recently MK-3475 was approved in US for advanced melanoma.

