#### 1.4 Tremelimumab Background

Tremelimumab (formerly CP-675,206) is a human immunoglobulin (Ig) G2 monoclonal antibody (mAb) being investigated as a cancer immunotherapeutic agent. Tremelimumab is specific for human cytotoxic T lymphocyte-associated antigen 4 (CTLA-4; cluster of differentiation [CD]152), a cell surface receptor that is expressed primarily on activated T cells and acts to inhibit their activation.

Summary of non-clinical experience: Tremelimumab has no cross-reactivity to related human proteins, or to mouse, hamster, rat, or rabbit CTLA-4, but it does demonstrate cross reactivity to cynomolgus monkey CTLA-4. Cytotoxic T lymphocyte-associated antigen 4 delivers a negative regulatory signal to T cells upon binding of B7.1 (CD80) or B7.2 (CD86) ligands on antigen-presenting cells. Tremelimumab completely blocks the interaction of human CTLA-4 with B7.1

IRB #: STU00202283-MOD0025 Approved by NU IRB for use on or after 2/8/2019 through 1/6/2020. and B7.2, resulting in increased release of cytokines (interleukin [IL]-2 and interferon [IFN]- $\gamma$ ) from human T cells, peripheral blood mononuclear cells (PBMCs) and whole blood, and cynomolgus monkey whole blood cultured in the presence of activating stimuli. In contrast, addition of tremelimumab to human whole blood in the absence of additional stimuli does not induce levels of cytokines in vitro that would be predictive of cytokine-release syndrome in vivo. In addition, tremelimumab shows minimal specific binding to constant fragment of antibodies (Fc) receptors, does not induce natural killer (NK) cell-mediated antibody-dependent cell-mediated cytotoxicity (ADCC) activity, and does not deliver inhibitory signals following plate-bound aggregation. As tremelimumab does not cross-react with mouse CTLA-4, an anti-mouse CTLA-4 surrogate mAb (9H10) was used to assess the antitumor activity of anti-CTLA-4 in the SA1N mouse model of fibrosarcoma. Antibody 9H10 demonstrated dose-dependent antitumor activity and, at the maximum dose tested, resulted in tumor regression in 4 of 5 treated animals. These animals were shown to be resistant to tumor rechallenge, demonstrating a durable antitumor immunity. Antitumor activity was observed in the model when antibody was present at a plasma concentration of 30 µg/mL. Thus, a concentration of 30 µg/mL 9H10 was identified as the target plasma concentration for tremelimumab.

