### 8.0 DRUG INFORMATION

# 8.1 MEDI4736

8.1.1 Other names Durvalumab

### 8.1.2 Classification - type of agent

MEDI4736, a human IgG1 $\kappa$  mAb directed against PD-L1, contains a triple mutation in the constant domain of the IgG1 heavy chain that reduces binding to C1q and the Fc $\gamma$  receptors

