# 8.1.3 Mode of action

MEDI4736 is being developed as a potential anticancer therapy for patients with advanced solid tumors. MEDI4736 is a human monoclonal antibody (MAb) of the immunoglobulin G1 kappa (IgG1 $\kappa$ ) subclass that inhibits binding of programmed cell death ligand 1 (PD-L1) (B7 homolog 1 [B7-H1], cluster of differentiation [CD]274) to programmed cell death 1 (PD-1; CD279) and CD80 (B7-1). MEDI4736 is composed of 2 identical heavy chains and 2 identical light chains, with an overall molecular weight of approximately 149 kDa. MEDI4736 contains a triple mutation in the constant domain of the immunoglobulin (Ig) G1 heavy chain that reduces binding to complement protein C1q and the fragment crystallizable gamma (Fc $\gamma$ ) receptors involved in triggering effector function.

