#### 8.2.3 Mode of action

Tremelimumab is a human IgG2 mAb directed against CTLA-4. Tremelimumab has an overall molecular weight of approximately 149 kDa including oligosaccharides. Cytotoxic T lymphocyte-associated antigen 4 is a critical regulatory signal for T-cell expansion and activation following an immune response, and it serves as a natural braking mechanism that maintains T-cell homeostasis. During T-cell activation, T cells upregulate CTLA-4, which binds to B7 ligands on antigen-presenting cells, sending an inhibitory signal that limits T-cell activation. Tremelimumab blocks the inhibitory signal resulting from CTLA-4 binding to B7, leading to prolongation and enhancement of T-cell activation and expansion.

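### Exclusion 3.2.22, the only explicit allergy criterion, refers to MEDI3475, an undefined code that matches neither study drug

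*Combined protocol and SAP*

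**What the plan says.** Section 3.2.22 excludes patients with a history of allergic reactions attributed to "compounds of similar chemical or biologic composition to MEDI3475 are not eligible". Section 3.0 makes the eligibility list binding: "Eligibility waivers are not" permitted, and a subject who meets any exclusion cannot be registered.

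The protocol gives each study drug one other name. Section 8.1.1 lists for MEDI4736 "Other names Durvalumab". Section 1.4 gives tremelimumab's former code, CP-675,206. In the same exclusion list, 3.2.18 (live vaccines) names both agents: "within 30 days of receiving either MEDI4736 or tremelimumab".

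**The concern.** The criterion defines a class of compounds by their similarity to a reference compound. If the reference is a code that the protocol never defines, the class has no stated anchor, and the person completing the eligibility check must guess what was meant.

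This matters because the criterion acts before the first dose. The protocol itself treats allergy history as relevant to risk: section 1.3.3.2 says severe allergic reactions are more common in subjects with a history of allergies, and section 7.2.4.2 notes that acute allergic reactions can be fatal. A rule that cannot be waived and that serves this purpose should identify the drugs the patient will receive.

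**Working it through.** There is no figure to reproduce and no arithmetic to run. The check is a comparison of texts.

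1. **Where the code occurs.** MEDI3475 occurs once, in 3.2.22. It is not in the list of abbreviations, the background, the drug information in section 8, or the change log in Appendix D. A few removed pages and the schema figure could not be checked, but they are unlikely places for a definition.

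2. **Comparison with the study drugs.** Section 4.1 gives the treatments as tremelimumab, MEDI4736, or both.

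| Name or code | Where | Equals MEDI3475? |
|---|---|---|
| MEDI4736 | throughout | no |
| Durvalumab | 8.1.1 | no |
| Tremelimumab | throughout | no |
| CP-675,206 | 1.4 | no |

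   The code therefore matches 0 of 2 study drugs.

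3. **Is it a scanning fault?** Unlikely. Set against MEDI4736, the digits differ in all four positions (3/4, 4/7, 7/3, 5/6). That is unlike MED14736 in section 4.2, where a letter I has become a 1.

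4. **Nearest other code.** Section 1.1.2 has the same four digits in a background sentence: "Recently MK-3475 was approved in US for advanced melanoma". That agent is not given in this trial.

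5. **Is it superseded text?** No. 3.2.22 is current. Amendments 2 to 5 changed eligibility criteria, and the log records no correction to this one.

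6. **Other allergy criteria.** None of the 15 inclusions (3.1.1 to 3.1.15) and none of the other 21 exclusions addresses allergy or hypersensitivity.

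7. **Who is already excluded by other rules.** 3.2.1 bars previous enrolment in this study. 3.2.2 bars prior anti-CTLA-4 therapy by name, which covers tremelimumab. It does not list anti-PD-L1 by name, but its wider wording takes in any agent aimed at T-cell co-stimulation or checkpoint pathways, which covers MEDI4736. A past reaction to either drug requires past exposure, so those patients are ineligible whatever 3.2.22 says.

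8. **Who is left for 3.2.22 to catch.** Mainly patients who reacted to some other similar biologic. For example, 3.2.6 admits patients treated with bevacizumab after a 4-week interval. Whether a reaction to such an agent counts as similar is not settled by the present wording and would not be settled by correcting the code.

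**The case against.** The strongest reply is that this is a slip any reader would repair. MEDI4736 is the only study drug with a MEDI code, and the rule covers a class of compounds, so it does not depend on a perfect label. The class could even reach tremelimumab. Section 8.1.3 describes MEDI4736, a human IgG1 antibody, as "with an overall molecular weight of approximately 149 kDa", and section 8.2.3 says that "Tremelimumab has an overall molecular weight of approximately 149 kDa including oligosaccharides". Other protections also exist. 3.2.20 gives the investigator discretion, and section 11.3 requires a signed checklist and a registration review before treatment. Sections 4.4, 8.1.11 and 8.2.7 provide infusion-reaction rules, emergency readiness and observation.

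Most of this stands, and it is why the point is minor. It does not make the criterion correct. Discretion under 3.2.20 is not an allergy rule, and infusion precautions act once dosing has begun. The checklist wording is not supplied, so whether it repeats the code is unknown. A reader should not have to argue from molecular weight that a criterion covers a study drug when 3.2.18 simply names both.

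Two stronger readings are tempting. A reader might infer that patients given tremelimumab in Arms 1 and 3 have no allergy screen. The documents do not support that: prior exposure to tremelimumab is already excluded, and the number of arms receiving it does not measure this defect. A reader might also infer, from the change log's mention of another company's template, that 3.2.22 was carried over from elsewhere. That entry concerns infusion-reaction rows in a table since replaced and says nothing about eligibility. The origin of the code is unknown, and the point does not need it.

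**Conclusion.** The criterion is wrong as written: a binding, non-waivable exclusion, and the only explicit one on allergy, is anchored to a code that identifies neither study drug. Confidence in the mismatch is high, because it rests on the text alone.

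The severity is minor. The conclusion that few patients are touched assumes that 3.2.2's wider wording is read to include anti-PD-L1 agents, which is its natural sense. No patient count can be derived, no effect on screening is shown, and there is no effect on sample size, power, alpha or endpoints.

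**What to change.** Reword 3.2.22 so that it excludes patients with a history of *allergic reactions attributed to MEDI4736, tremelimumab, or compounds similar to either in chemical or biologic composition*. Check that the eligibility checklist used at registration (section 11.3) carries the same wording.

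Adding the drugs' excipients is optional. Both products contain histidine, trehalose and polysorbate 80 (sections 8.1.4 and 8.2.9), so the addition has a basis, but it extends the rule beyond correcting the error and could make an occasional patient newly ineligible.

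The cost is one protocol line and one document check. Judging whether a past reaction to another biologic counts as similar stays with the clinician.
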